#### **6.5.4. Concomitant Medications and Non-Drug Treatments**

Per protocol, all concomitant medications, including prescription and nonprescription drugs, nondrug treatment, and dietary supplements and herbal preparations, will be entered on the case report form (CRF). Concomitant medications and treatments will be recorded from 28 days prior to the start of study treatment and up to 36 days post the last dose of study treatment or start of subsequent anticancer therapy (e.g., consolidation or conditioning regimen). Medications and treatments for the managements of VOD/SOS during the follow-up period are also to be collected.

Concomitant medications and non-drug treatments received by patients during the study will be summarized for the safety analysis set.

Concomitant medications refer to all medications which started prior to first dose of study treatment but continued during the on-treatment period (see Section 3.5) as well as those started during the on-treatment period (including starting on the date of the first dose of study drug). Concomitant medications will be coded in the WHO Drug coding dictionary and will be tabulated by Anatomical Therapeutic Chemical (ATC) Classification level 2 and preferred term in alphabetical order. A patient will be counted only once within a given drug class and within a given drug name, even if the same medication was received at different times. Preferred Terms will be reported under each ATC class that it is included under within WHO Drug (since no primary path is available in WHO Drug).

Concomitant non-drug treatments refer to all non-drug treatments administered during the on-treatment period (including on the date of the first dose of study drug). Non-drug treatments will be MedDRA coded and will be summarized by MedDRA SOC and PT alphabetical order. Patients will be counted only once per PT even if the same treatment was received multiple times.

Any medications which were only administered prior to treatment start will be summarized for the safety analysis set by WHO Drug coding dictionary preferred term in alphabetical order.

Any non-drug treatments, aside from anti-cancer treatments described in Section 6.5.1.4, which were only administered prior to treatment start will be listed as needed to be compliant with ICH required listings but not summarized.

Transfusions: for each of the two transfusion types (Packed RBC and Platelets) the number of days with a transfusion during the on-treatment period for each cycle will be computed for each patient. For each cycle, each transfusion type will be summarized with summary statistics (n, mean, median, standard deviation, minimum, and maximum) of the number of days with transfusion. Additionally, the number of days will be categorized as (<=7 days, 8-14, 15-21, 22-28, 29-36, >36) and the number and percent of patients in each category will be summarized.

#### **6.5.5. Follow-up Anti-cancer Treatments**

Summaries will be for the full analysis set.

Follow-up anti-cancer systemic therapies will be identified as therapies with start date after the last dose of study treatment.

A summary of number of follow-up regimens according to the number and percentage of patients with 1, 2, 3, or >3 induction regimens will be provided.

A summary of the number and percentage of patients with at least one follow-up regimen, and the number of patients with at least one induction regimen, at least one conditioning regimen, at least one consolidation or intensification regimen, and at least one maintenance regimen will be provided.

Follow-up radiation treatments will be identified by start date after the last dose of study treatment. A summary of the number and percentage of patients with at least one follow-up radiation treatment given for conditioning, and the number and percentage of patients with at least one follow-up radiation treatment for other reasons will be provided.

Follow-up HSCT will be identified by start date after to the last dose of study treatment. The number and percentage of patients with at least one follow-up HSCT and a summary of patients according to the number of follow-up HSCT (1, >1) (number and percentage) will be provided. Follow-up HSCT will be identified by HSCT date after the last dose of study treatment. If a patient has more than one follow-up HSCT, then the first HSCT after to study treatment will be included in the summary.

For the patients with a follow-up HSCT a summary of the following characteristics (number and percentage) using patients with a follow-up HSCT as the denominator will be provided.

Each of the following aspects will be summarized according to the categories collected on the CRF.

- Time of transplant relative to last GO dose (< 2 mos or  $\geq$  2 mos after the last dose of GO)
- Type of transplant
- Donor relatedness
- HLA compatibility
- Stem Cell Source
- Type of conditioning
- Disease Risk at Transplant

## 6.6. Safety Summaries and Analyses

Safety (AE and other parameters) summaries will be provided for the safety analysis set unless otherwise specified.

### 6.6.1. Adverse Events

The following general considerations will be applied to AE summaries:

All analyses will be based on treatment emergent events unless otherwise specified. Treatment emergent is defined in Section 3.5.1. AEs not considered treatment emergent will be flagged in data listings (as applicable to listings needed to be compliant with ICH required listings).

- For summaries including CTCAE grade, patients will be counted according to the worst grade for the particular PT or SOC and will also include a total across grades.
- For summaries including toxicity grade, as described in Section 5.3.2, in the case that a patient has events with missing and non-missing toxicity grades, the maximum of the non-missing grade will be displayed. Missing grade will only be displayed in the event that only one event has been reported for a patient and the grade is missing.
- There will also be a row for the number and percentage of patients reporting at least 1 AE.
- For summaries including SOC, the number and percentage of patients with at least 1 AE in that SOC will be reported.
- The denominator for percentages will be the number of patients treated in the group being summarized.
- Each patient will be counted only once within each SOC and PT.
- In summaries of treatment related AEs, if the relationship to study treatment is missing on the CRF, it will be assumed to be related to treatment.

A high level summary of adverse events (all causality and also for treatment related events) will include the number and percentage of patients with:

- Any Adverse Event
- Serious AE

- Adverse Events with CTCAE Grade 3-4
- Grade 5 events
- AEs that caused the subject to be discontinued from the study
- AEs with Action Taken with Study Treatment was Drug Withdrawn but AE did not Cause the Subject to be discontinued from the study
- AEs leading to dose reductions or temporary discontinuations (note that no dose reductions are specified per protocol and the CRF used the term interruptions rather than temporary discontinuations)
- Additionally, the number of events will be provided. Each unique adverse event at the PT level for a patient is included in the count.

Seriousness, toxicity grade, action taken will be as reported by the investigator on the adverse event CRF.

**Summaries by SOC and PT** in decreasing frequency within SOC based on frequencies observed for adult patients will be provided for:

- Treatment Emergent Adverse Events by Maximum CTCAE Grade (All Causality); (which will have a column for each of the grades)
- Treatment Emergent Adverse Events by Maximum CTCAE Grade (Treatment Related);
- Serious Treatment Emergent Adverse Events (All Causality);
- Serious Treatment Emergent Adverse Events (Treatment Related);

The summary of Treatment Emergent Adverse Events by SOC, PT, and Maximum CTCAE Grade (All Causality); will also be provided by Cycle (1, 2, and Follow-up) CCI

Each AESI defined in Section 3.5.1.1 will be summarized by PT and Maximum CTCAE Grade (All Causality) (which will have a column for each of the grades)

The AESI of INFUSION RELATED REACTIONS (including Anaphylaxis) will also be summarized for by ADA status (patients overall ADA positive and patients ADA negative).

**Summaries by PT only** (i.e. summaries will not include SOC) in decreasing frequency based on the frequencies observed for adult patients for the following: Cutoffs in terms of percentage of events such as  $\geq 10\%$  in any patient group or number of patients (SAE tables such as 2 adult patients) may be applied.

- Treatment Emergent Adverse Events Leading to Study Drug Withdrawal (ie based on last action taken for study drug; not study discontinuation) (All causality) by Maximum CTCAE grade showing at least Grade 5.
- Treatment Emergent Adverse Events Leading to Study Drug Withdrawal (ie based on last action taken for study drug; not study discontinuation) (Treatment Related) by Maximum CTCAE grade showing at least Grade 5.
- Treatment Emergent Adverse Events Leading to Study Drug Interruption (All causality)
- Treatment Emergent Adverse Events Leading to Study Drug Interruption (Treatment Related)
- Treatment Emergent Adverse Events by Maximum CTCAE Grade (All Causality) with grouped grades such as Grade 1-2; Grade 3-4; Grade 5; Grade  $\geq 3$  with a cutoff such as  $\geq 10\%$  of any patient group
- Treatment Emergent Adverse Events by Maximum CTCAE Grade (Treatment Related) with grouped grades such as Grade 1-2; Grade 3-4; Grade 5; Grade  $\geq 3$  with a cutoff such as  $\geq 10\%$  of any patient group
- Serious Treatment Emergent Events (All Causality) with a cutoff such as  $\geq 2$  adult patients
- Serious Treatment Emergent Events (Treatment Related) with a cutoff such as  $\geq 2$  adult patients

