6.2.2.4. Cycle 1 Days 15 and 21 (Post-GO Period)

- Laboratory tests (except CBC and differential counts) will be conducted according to [Schedule of Activities \(Table 1\)](#).
- Starting with Day 15, CBC and differential counts will be examined 3 times a week until having determination of remission status (see [Section 7.5](#)); subsequently CBC and differential counts will be collected once weekly until EOT visit (ie, 36 days after the last dose of GO) or until start of subsequent anticancer therapy, eg, Cycle 2, consolidation and/or conditioning regimen (see [Schedule of Activities Table 1](#)).
- Pharmacokinetic (all patients) ^{CC1} according to [Schedule of Activities \(Table 2\)](#).
- Blood sample will be collected for the measurement of antibodies to GO (ADA) and neutralizing antibody (NAb) on Days 15 and 21.
- Patients with extramedullary disease during screening or clinically suspicious after GO near the scheduled day for bone marrow aspiration (and biopsy if applicable) will have imaging assessment (eg, CAT or MRI). (Day 21)
- Efficacy evaluation and determination of remission status will be assessed by peripheral blood and bone marrow aspiration (and biopsy if applicable) after recovery of blood counts is observed, typically between Day 21 and Day 28. This evaluation should be conducted prior to Cycle 2 (if administered) or EOT (ie, 36 days after last the dose of GO).
- Adverse events should be documented and recorded using NCI CTCAE version 4.03 (see [Section 8](#)).
- Concomitant medications and treatments will be recorded.

6.2.3. Cycle 2

The second cycle will be allowed at the investigator's discretion for patients who meet selected dosing criteria after Cycle 1 (see [Section 7.5](#)). Cycle 2 Day 1 must be started no later than 42 days after the last dose of GO (ie, Cycle 1 Day 7).

6.2.3.1. Cycle 2 Day 1

- On Day 1 patients may be admitted at the site for 24 hours as per investigator's discretion. Hospitalization beyond Day 1 will be per standard practice and investigator judgment. If there is prolongation of hospitalization, consider if SAE criteria are met (see [Section 8.2.4](#)).

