		The high level summary of AEs was updated, and summary tables of AE that had actions taken due to the AE were added. Additional summaries were added for in-text tables.	The update is consistent with current standard tables and oncology reporting conventions. Updates to AE summaries were made to facilitate production of in-text CSR tables consistent with recently updated oncology conventions.
		A summary of AESI of INFUSION RELATED REACTIONS by ADA status was added.	The summary was added to assess the impact of ADA on safety.
		Laboratory summaries were changed from worst (maximum) grade to shift from baseline tables; similarly non-CTC graded laboratory summaries were changed to shift, and summary of liver function tests was added.	Updates to summaries were made to facilitate production of in-text CSR tables and consistent with recently updated oncology conventions.
		ECG maximum increase from baseline as a continuous variable summarized with descriptive statistics was removed.	It was considered sufficient to summarize this categorically.

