### **3.5.1.1. Adverse Events of Special Interest (AESI)**

Certain AEs will be grouped together to support discussion of AEs of Special Interest, these will be reported as clusters using the MedDRA coding as follows with the specific definitions provided in Appendix 2:

- MYELOSUPPRESSION
- HEAMORRHAGE
- INFECTION (Grade  $\geq 3$  and/or serious infection)
- HEPATOTOXICITY (Grade  $\geq 3$  and/or serious hepatotoxicity including all VOD/SOS)
- INFUSION RELATED REACTIONS (including Anaphylaxis): From start of infusion to within 24 hours of end of infusion
- TUMOUR LYSIS SYNDROME
- CARDIAC CONDUCTION

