#### 6.2.2. Immunogenicity

Immunogenicity will be summarized for the immunogenicity analysis set (as defined in Section 4.4.4).

The percentage of patients with positive ADA and NAb will be summarized (eg. at baseline, treatment-induced (positive for the first time after dosing), and treatment-boosted (pre-existing positive titers that were at a higher level post-baseline), and overall (treatment-induced + treatment-boosted). The overall percentage will be computed excluding baseline positive patients without any post-dose assessment. The other percentages will be based on the number of patients in the immunogenicity analysis set.

For patients with positive ADA/NAb, the magnitude of the titer will be described with summary statistics (median, Q1, Q3) for positive baseline titers, peak titer for treatment-induced and treatment-boosted, and titer fold increase for treatment-boosted (calculated as the ratio of peak post-dose titer to baseline titer), if data permit.

For patients with treatment induced ADA/NAb, time of onset, and duration will also be described with summary statistics (median, Q1, Q3), if data permit. Onset of ADA/NAb will be calculated as date of first positive result – date of first dose +1. Duration of ADA/NAb will be calculated as date of last positive result – date of first positive result +1. The number and percent of transient and persistent positive ADA/NAb will be summarized out of the number of patients with treatment-induced ADA/NAb.

Transient ADA/NAb will be defined as treatment-induced ADA/NAb meeting the following conditions:

- detected only at one sampling time point during the treatment or follow-up (excluding the last sampling time point which will be considered persistent unless shown to be undetectable at a later time) or
- detected at two or more sampling time points during the treatment (including follow-up), where the first and last positive samples (irrespective of any negative samples in between) are separated by a period less than 16 weeks, and the last sampling time point is negative

Persistent ADA/Nab will be defined as treatment-induced ADA/NAb meeting the following conditions:

- detected at two or more sampling time points during the treatment (including follow-up), where the first and last positive samples (irrespective of any negative samples in between) are separated by a period of 16 weeks or longer or

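### The infusion-reaction table by ADA status sorts Cycle 1 reactions by a status settled only after their windows close, and does not place unboosted baseline-positive patients

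*SAP*

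**What the plan says.** SAP 6.6.1 (Adverse Events) plans that infusion-related reactions, including anaphylaxis, will be "summarized for by ADA status (patients overall ADA positive and patients ADA negative". The summary is not split by cycle or by the time at which ADA was found. SAP Table 1 gives its purpose: "The summary was added to assess the impact of ADA on safety". SAP 6.2.2 refers to 6.6.1 for the impact of ADA on safety.

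The patient-level meaning of overall positive is in SAP 6.2.2: "overall (treatment-induced + treatment-boosted". Its two parts are "treatment-induced (positive for the first time after dosing" and "treatment-boosted (pre-existing positive titers that were at a higher level post-baseline". SAP 3.2.2 calls a titer below 75 negative and any other titer positive, but gives no patient-level rule for someone who is positive at baseline and not boosted.

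On timing, Protocol 6.2.2.1 has a pre-dose ADA sample on Cycle 1 Day 1, and Protocol 6.2.2.4 has the next ones: "Blood sample will be collected for the measurement of antibodies to GO (ADA) and neutralizing antibody (NAb) on Days 15 and 21". The reaction window in SAP 3.5.1.1 runs "From start of infusion to within 24 hours of end of infusion". Infusions are on Days 1, 4 and 7 of each cycle, and Cycle 2 is optional.

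**The concern.** A table meant to show whether ADA affects infusion reactions should sort patients by ADA status at or before the infusion. Here the positive label can be given only after every Cycle 1 infusion is over. One group that is known to carry ADA at the first infusion, the baseline-positive patients without a later rise, is not in the positive column at all. If those patients fall into the negative column, any excess of reactions among them would raise the comparator rate.

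An unexpected serious risk of anti-drug antibodies is among the post-marketing requirement topics in the Protocol Summary. A table showing no difference could therefore carry more weight with a reader than its construction allows.

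**Working it through.** The documents state no figure for this table, so there is none to reproduce. The check sets the sampling days against the reaction windows.

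**Inputs.** Infusion days 1, 4 and 7 (Protocol 3). A dose is omitted if delayed by more than 2 days (Protocol Table 3). The window ends 24 hours after the end of infusion (SAP 3.5.1.1) and is compared by date only (SAP Appendix 2). The first post-dose ADA sample is on Day 15, with a ±1 day visit window, so on Days 14 to 16 (Protocol Table 2 and 6.2.2.4).

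**Gap** = day of first post-dose sample − day on which the last Cycle 1 window closes.

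| Last Cycle 1 infusion | Window closes | First sample | Gap (days) |
|---|---|---|---|
| Day 7 (on time) | Day 8 | Day 14 to 16 | 6 to 8 |
| Day 9 (one 2-day delay) | Day 10 | Day 14 to 16 | 4 to 6 |
| Day 11 (two delays that add up) | Day 12 | Day 14 to 16 | 2 to 4 |

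The gap is positive in every row. Protocol 7.2.1 describes later samples, from Day 10 on, as mainly for immunogenicity, but the Day 10 procedures in 6.2.2.3 list no ADA sample. Even a Day 10 sample (±1, so Day 9 at the earliest) would follow the Day 8 close when dosing is on time. An end-of-treatment visit brought forward for new therapy also comes after the patient's last infusion.

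**Share of infusions before the first post-dose sample.** One-cycle patient: 3/3 = 100%. Two-cycle patient: 3/6 = 50%.

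**Placement of patients.**
- Baseline negative, later positive: induced, so overall positive.
- Baseline positive, titer rises: boosted, so overall positive. ADA was detected before the first infusion.
- Baseline positive, titer does not rise: neither induced nor boosted, so not overall positive. Whether such a patient is negative or dropped is not stated.
- Baseline negative, no post-dose sample: SAP 4.4.4 needs only one sample with a result, and SAP 6.2.2 excludes only baseline-positive patients without a post-dose assessment. This patient could be counted negative untested.

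**Illustration; every input is assumed.** Take 50 adults and Cycle 1 reactions only. Reaction risk is 0.60 with ADA at infusion and 0.20 without, a true ratio of 3.0. Let b be the unboosted baseline positives and k the patients whose ADA arises after Cycle 1 dosing, with no boosted patients. The positive column then has risk 0.20. If the b patients are counted negative, that column has risk [(50 − b − k) × 0.20 + b × 0.60] / (50 − k).

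- b = 2, k = 2: (9.2 + 1.2)/48 = 0.217; ratio 0.20/0.217 = 0.92.
- b = 5, k = 5: (8.0 + 3.0)/45 = 0.244; ratio 0.82.
- b = 8, k = 5: (7.4 + 4.8)/45 = 0.271; ratio 0.74.
- b patients dropped: ratio 0.20/0.20 = 1.0.

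Boosted patients change this. Keep b = 5 and 5 overall positives, but let 3 of those be boosted and 2 late. The positive column has (3 × 0.60 + 2 × 0.20)/5 = 0.44. The ratio is 0.44/0.244 = 1.8 with the b patients counted negative, or 0.44/0.20 = 2.2 with them dropped. The result thus turns on the mix of patient types and on an unstated counting rule.

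**Group size.** At an assumed ADA incidence of 2% to 20%, the positive column holds 50 × 0.02 = 1 to 50 × 0.20 = 10 adults.

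**The case against.** A reader might infer that the table cannot show any effect of ADA. The documents do not support that. Boosted patients had ADA detected in the pre-dose sample and are in the positive group, so overall status does not rest on post-dose samples alone. Cycle 2 infusions follow the Day 15 and Day 21 samples. First detection on Day 15 also does not date onset: ADA may or may not have been present on Day 4 or Day 7. These points stand. They mean that the table mixes ordered and unordered information, not that it holds none.

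A reader might also take this to be the only analysis of ADA and safety. It is the only visible one, but SAP 6.6.1 contains redacted text, so this cannot be established.

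Reverse causation is another tempting inference: reactions lead to fewer doses, and so to less ADA. Protocol Table 3 does link severe reactions to discontinuation, but nothing in the documents says that fewer doses induce less ADA.

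The practical stakes are limited. The summary is descriptive, with no test or decision rule, and the secondary endpoint of ADA and neutralizing-antibody incidence is unaffected. SAP 6.2.2 also reports the percentage positive at baseline and, if data permit, onset for induced ADA, so some timing information will sit beside the table. The unboosted group may be very small or empty: no pre-existing ADA rate is given, and prior treatment with the drug is an exclusion.

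The core point survives all of this. The pooled table does not let the reader separate correctly ordered from incorrectly ordered exposure, and the counting rule is missing.

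**Conclusion.** The point holds in a limited form. Overall positive status cannot be established until 2 to 8 days after the last Cycle 1 reaction window has closed (6 to 8 days with on-time dosing). That covers all 3 infusions of a one-cycle patient and 3 of 6 for a two-cycle patient. Unboosted baseline-positive patients are outside the positive group, and their placement is unspecified. The planned table is therefore a weak basis for assessing the impact of ADA on safety, although the data collected can support something better.

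This rests on reading overall positive in SAP 6.6.1 as the term defined in SAP 6.2.2, the only patient-level definition visible, and on ADA sampling as listed in the visit procedures. The size of any distortion is unknown. The ratios above come from assumed inputs, and the documents do not support a claim that a real effect would be hidden or reversed. The primary analysis is untouched. This is a worthwhile, inexpensive correction to a descriptive safety summary.

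**What to change.** In SAP 6.6.1, add or substitute two time-ordered summaries:

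1. Reactions at Cycle 1 infusions, by baseline (pre-dose Day 1) ADA status.
2. Reactions at Cycle 2 infusions, by ADA status before Cycle 2 Day 1, counting any positive at or before the last sample preceding that day (normally Day 21, or Day 15 if Day 21 is missing).

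State where unboosted baseline-positive patients and patients with no post-dose sample are counted. If the current table stays, footnote it to say that ADA status was mostly determined after the reactions.

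The cost is SAP wording and one or two tables from data already collected, with no new sampling. The limits should be stated too. Cells will be small, and the first summary may have few or no baseline positives. The second covers only patients selected for Cycle 2 by the marrow and blood-count criteria and by investigator discretion. Both remain descriptive and would not settle causation.
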